## **15.1 RESEARCH PARTICIPANT REGISTRATION AND RANDOMIZATION PROCEDURES**

### **15.2 Research Participant Registration**

Confirm eligibility as defined in the section entitled Criteria for Patient/Subject Eligibility.

Obtain informed consent, by following procedures defined in the section entitled Informed Consent Procedures.

During the registration process registering individuals will be required to complete a protocol specific Eligibility Checklist.

The individual signing the Eligibility Checklist is confirming that the participant is eligible to enroll in the study. Study staff are responsible for ensuring that all institutional requirements necessary to enroll a participant to the study have been completed. See related Clinical Research Policy and Procedure #401 (Protocol Participant Registration).

#### **15.2.1 Registration for Participating Sites:**

Central registration for this study will take place through MSK's Clinical Trials Management System (CTMS).

To complete registration and enroll a participant from another institution, the site must first contact the MSK study coordinator to notify him/her of the participant registration.

Once the MSK study coordinator is notified, the site will document the participant's consent by associating the participant to the protocol in CTMS. This will generate a study ID number that is unique and must be written on all data and correspondence for the participant.

After associating the participant to the protocol, the site will enter the consent status in real-time, but no later than 2 business days, from when the informed consent was signed.

The following documents must be saved to CTMS within 2 business days of documenting consent status:

- The completed or partially completed MSK eligibility checklist
- The signed informed consent and HIPAA Authorization form

Supporting source documentation for eligibility questions (e.g. laboratory results, pathology report, radiology reports, MD notes, physical exam sheets, medical history, prior treatment records, and EKG report) will be sent to the MSK study coordinator within 30 days of consent so eligibility can be verified. Once the MSK study coordinator verifies eligibility the site will be notified to enter eligibility and on study status in CTMS, which will complete participant registration.

#### **15.3 Randomization**

This study does not involve randomization.

### **16.1 DATA MANAGEMENT ISSUES**

All experimental data including TcL, ICG mapping and detection, nodal ICG and TcL measurements and correlating pathology results will be stored in a REDCap database. Data from patients accrued at other institutions will also be submitted to the secure REDCap

database. External institutions will only have access to patient information submitted from their respective institution. The PI and MSK research team will be the only researchers with access to other institutions data submissions.

Data will be managed through REDCap (Research Electronic Data Capture), a data management software system supported by Clinical Research Administration at MSK. Members of the Clinical Research Administration supporting the REDCap software will have access to the data for the purpose of ensuring the proper functioning of the database and the overall software system. REDCap is a tool for the creation of customized, secure data management systems including web-based data entry forms, reporting tools, and a full array of security features including user and group based privileges with a full audit trail of data manipulation and export procedures. REDCap is maintained on MSK-owned servers that are kept in a locked server room with appropriate environmental modifications (e.g., special air conditioning), supported by an uninterrupted power supply, and backed up nightly with some backup tapes stored off-site. All connections to REDCap utilize encrypted (SSL-based) connections. Nationally, the REDCap software is developed, enhanced, and supported through a multi-institutional consortium led by the Vanderbilt University CTSA. REDCap will only be used for the housing of survey data. Use of REDCap has been approved by the department's manager of IT Systems and by MSK Information Security.

#### **16.1.1 Data and Source Documentation for Participating Sites**

##### **Data**

The participating site(s) will enter data onto a standardized data collection CRF. Data entry guidelines have been generated for this study and blank data collection CRFs will be sent to the study staff at each participating site for use. The participating site PI is responsible for ensuring these forms are completed accurately, legibly and in a timely manner.

The participating site(s) will enter data remotely into an electronic database using the internet based system, REDCap. Data entry guidelines have been generated for this study and site staff will receive database training prior to enrolling its first participant. The participating site PI is responsible for ensuring these forms are completed accurately and in a timely manner. A schedule of required forms is shown in section 16.0.3.

##### **Source Documentation**

Source documentation refers to original records of observations, clinical findings and evaluations that are subsequently recorded as data. Source documentation should be consistent with data recorded on CRFs and entered into the REDCap database. Relevant source documentation to be submitted throughout the study includes:

- Diagnosis
- Patient history/MD notes
- Operative reports

Source documentation should include a minimum of two identifiers to allow for data verification. MSK will maintain the confidentiality of any subject-identifiable information it may encounter.

### **16.1.2 Data and Source Documentation Submission for Participating Sites**

Participating sites should email source documentation to MSK at the contact information provided by the MSK study coordinator. Submissions should include a cover page listing all documents enclosed per participant.

Participating sites should enter data directly into REDCap and study-specific paper CRFs. Source documentation should be sent to MSK at the contact information provided by the MSK study coordinator. Submissions should include a cover page listing relevant records enclosed per participant.

### **16.1.3 Data and Source Documentation Submission Timelines for Participating Sites**

Data and source documentation to support data should be transmitted to MSK according to chart 2.

**Chart 2: Data and Source Submission Requirements and Timelines**

	Baseline	Visit 1	Visit 2	Visit 3	SAE	Off Study
Submission Schedule						
Source Documentation	Within 2 days (see section 13.1.1 )		Within 14 days of visit if diagnostic or other clinical protocol		Within 3 days of event updates to be submitted as available	Within 14 days of visit if diagnostic or other clinical protocol
REDCap eCRFs	Within 7 days of visit					
Required Forms						
SAE Form					X	

## **16.2 Quality Assurance**

Completeness of registration data will be monitored by the clinical research coordinator on a regular basis. Routine data quality reports will be generated to assess missing data and inconsistencies. Accrual rates, and the extent and accuracy of evaluations and follow-up, will be monitored periodically throughout the study. Potential problems will be brought to the attention of the study team for discussion and action. Random-sample data quality and protocol compliance audits will be conducted by the study team at a minimum of twice per year, or more frequently if indicated.

### **16.2.1 Quality Assurance for Participating Sites**

Each site accruing participants to this protocol will be audited by the staff of the MSK study team for protocol and regulatory compliance, data verification and source documentation.

Audits will be conducted annually during the study (or more frequently if indicated) and at the end or closeout of the trial. Ideally the first audit will occur shortly after the first patients are enrolled. The number of participants audited will be determined by auditor availability and the complexity of the protocol. Each audit will be summarized and a final report will be sent to the PI at the audited participating site within 30 days of the audit.

### **16.3 Data and Safety Monitoring**

The Data and Safety Monitoring (DSM) Plans at Memorial Sloan Kettering Cancer Center were approved by the National Cancer Institute in September 2001. The plans address the new policies set forth by the NCI in the document entitled “Policy of the National Cancer Institute for Data and Safety Monitoring of Clinical Trials” which can be found at: <http://www.cancer.gov/clinicaltrials/conducting/dsm-guidelines/page1>. The DSM Plans at MSKCC were established and are monitored by the Office of Clinical Research. The MSKCC Data and Safety Monitoring Plans can be found on the MSKCC Intranet at: <http://inside2/clinresearch/Documents/MSKCC%20Data%20and%20Safety%20Monitoring%20Plans.pdf>

There are several different mechanisms by which clinical trials are monitored for data, safety and quality. There are institutional processes in place for quality assurance (e.g., protocol monitoring, compliance and data verification audits, therapeutic response, and staff education on clinical research QA) and departmental procedures for quality control, plus there are two institutional committees that are responsible for monitoring the activities of our clinical trials programs. The committees: *Data and Safety Monitoring Committee (DSMC)* for Phase I and II clinical trials, and the *Data and Safety Monitoring Board (DSMB)* for Phase III clinical trials, report to the Center’s Research Council and Institutional Review Board.

During the protocol development and review process, each protocol will be assessed for its level of risk and degree of monitoring required. Every type of protocol (e.g., NIH sponsored, in-house sponsored, industrial sponsored, NCI cooperative group, etc.) will be addressed and the monitoring procedures will be established at the time of protocol activation.

### **16.4 Regulatory Documentation**

Prior to implementing this protocol at MSK, the protocol, informed consent form, HIPAA authorization and any other information pertaining to participants must be approved by the MSK Institutional Review Board/Privacy Board (IRB/PB). There will be one protocol document and each participating site will utilize that document.

The following documents must be provided to MSK before the participating site can be initiated and begin enrolling participants:

- Participating Site IRB approval(s) for the protocol, appendices, informed consent form and HIPAA authorization
- Participating Site IRB approved informed consent form
- Participating Site IRB's Federal Wide Assurance (FWA) number and OHRP Registration number
- Curriculum vitae and medical license for each investigator and consenting professional
- Documentation of Human Subject Research and Good Clinical Practice Certification for investigators, consenting professionals and key study personnel at the participating site.

For interventional studies funded by the NIH, GCP training must be renewed every 3 years.

Upon receipt of the required documents, MSK will formally contact the site and grant permission to proceed with enrollment.

#### **16.4.1 Amendments**

Each change to the protocol document must be organized and documented by MSK and approved first by the MSK IRB/PB. Protocol amendments that affect MSK only (e.g. change in MSK Co-Investigator, MSK translation, etc.) do not require IRB review at the participating site(s). All other protocol amendments will be immediately distributed to each participating site upon receipt of MSK IRB/PB approval.

Each participating site must obtain IRB approval for all amendments within 90 calendar days of MSK IRB/PB approval. If the amendment is the result of a safety issue or makes eligibility criteria more restrictive, participating sites will not be permitted to continuing enrolling new participants until site IRB approval of the revised protocol documents is granted and submitted to MSK.

Each participating site must provide all site IRB approvals for amendments/modifications and the most current approved version of the site informed consent form and HIPAA authorization at the time of approval. Documents must be submitted to MSK on a continuing basis.

#### **16.4.2 Additional IRB Correspondence**

##### Continuing Review Approval

The Continuing Review Approval letter from the participating site's IRB and the most current approved version of the informed consent form and HIPAA authorization must be submitted to MSK within 7 days of expiration. Failure to submit the re-approval in the stated timeline will result in suspension of new participant enrollment.

##### Deviations

A protocol deviation on this study is defined as any incident involving non-adherence to an IRB approved protocol. Deviations typically do not have a significant effect on the rights, safety, or welfare of research participants or on the integrity of the resultant data. Deviations that represent unanticipated problems involving risks to participants or others, or serious adverse events must be reported according to sections 17.2.1.

Deviations that do not adversely affect the rights and/or welfare of the participant or the scientific validity of the study and are related to protocol scheduling changes outside of the allowed window due to a holiday (e.g., New Year's, Thanksgiving, etc.) and/or inclement weather or other natural event do not require reporting to the MSK IRB/PB. However, they must be clearly documented in the patient's medical record.

##### *Prospective Deviations*

Deviations to the research protocol that involve patient eligibility, an informed consent procedure change, and/or treatment/pharmacy alterations that are not allowed by the protocol require prospective approval from the MSK IRB/PB prior to the change being carried out. Participating sites must contact the MSK PI who will in turn seek approval from the MSK IRB/PB.

#### *Retrospective Deviations*

Deviations that include a change or departure from the research protocol without prior approval from the MSK IRB/PB are considered retrospective deviations. Retrospective deviations must be reported to the MSK PI as soon as possible, who will in turn report the deviation to the MSK IRB/PB as per MSK guidelines.

#### *Participating Site IRB Reporting*

Participating sites must report all deviations to their institution's IRB per local guidelines. Approvals/acknowledgments from the participating site IRB for protocol deviations must be submitted to MSK upon receipt.

#### Other correspondence

Participating sites must submit other correspondence to their institution's IRB according to local guidelines, and submit copies of all site IRB correspondence, including approvals and acknowledgements, to MSK.

#### **16.4.3 Document maintenance**

The MSK PI and participating site PI will maintain adequate and accurate records to enable the implementation of the protocol to be fully documented and the data to be subsequently verified.

The participating sites will ensure that all regulatory documents and participating site IRB correspondences are maintained in an onsite regulatory binder and are sent to MSK as outlined within the protocol. A regulatory binder for each site will also be maintained at MSK; this binder may be paper or electronic.

After study closure, the participating sites will maintain all source documents, study related documents and CRFs for 3 years.

#### **16.5 Noncompliance**

If a participating site is found to be noncompliant with the protocol document, accrual privileges may be suspended and/or contract payments may be withheld (if applicable), until the outstanding issues have been resolved.

### **17.1 PROTECTION OF HUMAN SUBJECTS**

Participation in this trial is voluntary. All patients or their legal guardians will be required to sign a statement of informed consent, which must conform to MSKCC IRB guidelines. The informed consent must contain a full explanation of the possible advantages, benefits, risks,

alternative treatment options, and availability of treatment in the case of injury, in accordance with Federal Regulations as detailed in 21CFR50. The investigator is responsible for obtaining written informed consent from potential patients or legal guardian before performing any trial tests or assessments required by the protocol. A copy of the signed document will be given to the patient or legal guardian , and the original will be retained by the investigator with his/her copy of the record forms.

Given the nature of these tumors, most patients will be children, adolescents, and young adults. Patients of both sexes and all racial/ethnic backgrounds are eligible for this study. Alternative treatments are available and will be discussed with the patient or legal guardian.

**Benefits:** This study is not expected to help treat the cancer, but it may lead to removal of extra lymph nodes for analysis. What we learn from this study may help patients in the future.

**Risks:** The potential risks of this therapy as described in section 11 of this protocol may outweigh the potential benefits in an individual patient. The potential risks are related to the adverse effects which could be induced by the ICG dye.

Patients or their legal guardians will be charged for the costs for all routine visits, treatment, and non-research testing related to the cancer. Patients will not be charged for the ICG dye, the preparation, or for use of the specialized camera used as part of the study.

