## 2.1 OBJECTIVES AND SCIENTIFIC AIMS

- Primary Objective
  - Show that the SLN detection rate using ICG-guided transdermal lymphography is not inferior to that of TcL in pediatric solid tumors
- Secondary Objectives
  - Safety of ICG injection
  - Compare the total number of ICG+ and TcL+ SLNs harvested in each patient
  - Compare the percent of patients who have a pathologically positive SLN identified with each technique (sensitivity rate)

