## 4.1 OVERVIEW OF STUDY DESIGN/INTERVENTION

### 4.2 Design

This is a prospective, multi-institutional clinical trial to evaluate non-inferiority of ICG-guided SLN biopsy compared with the gold standard TcL-guided SLN biopsy in pediatric patients with solid tumors. Each patient will undergo TcL, consistent with the standard of care, but the surgeon will be blinded to the results preoperatively. Intraoperatively, ICG injection and transdermal lymphography will be used to identify the draining nodal basin and the position of the sentinel nodes. ICG transdermal lymphography will be considered successful if SLNs can be visualized on near-infrared imaging. After the transdermal lymphography results have been recorded, the surgeon will be unblinded to the TcL mapping. All ICG-positive and TcL-positive nodes will be removed and complete excision will be confirmed by intra-operative near-infrared imaging and gamma probe evaluation. Thus, in this trial each patient will serve as his/her own control. If TcL fails, no repeat TcL will be performed, the SLN biopsy will be done with ICG alone, and the patient will be recorded as a failure of TcL (i.e. decreasing the detection rate for TcL). If ICG mapping fails, the TcL results will be used to perform SLN biopsy and the patient will be considered a failure of ICG (i.e. decreasing the detection rate for ICG). In the <1% of patients that fail both TcL and ICG, no SLN biopsy will be performed and the patient will be recorded as a failure of both TcL and ICG. These patients will still contribute data to the primary endpoint (i.e. decreasing the detection rate for both modalities) and safety data, but will not contribute to the other secondary aims. Approximately 59 patients will be enrolled over a period of approximately 4 years.

The primary outcome, SLN detection rate, will be compared between ICG-guided transdermal lymphography and TcL to determine non-inferiority of ICG in this clinical application. Secondary outcomes include the safety of ICG in this clinical scenario, comparisons of the total number of excised nodes identified with each detection method in each patients, and the sensitivity rate (percent of patients with a pathologically positive SLN) for each technique.

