### **Secondary objectives**

Safety will be analyzed with descriptive statistics of the number and type of adverse reactions encountered (per CTCAE guidelines).

The number of nodes identified by each technique will be compared using a paired Wilcoxon signed-rank test.

To evaluate sensitivity, the percent of patients in whom a SLN is found to contain tumor on pathology using each technique will be compared with McNemar's test for matched pair data.

Finally, to determine whether the intensity of each node is associated with pathologic positivity, a logistic regression model will be fit with pathologic positivity as the outcome and intensity as the predictor, and robust standard errors will account for correlation among multiple nodes per patient. This will be done separately for ICG and TcL intensity.

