## **17.3 Serious Adverse Event (SAE) Reporting**

An adverse event is considered serious if it results in ANY of the following outcomes:

- Death
- A life-threatening adverse event
- An adverse event that results in inpatient hospitalization or prolongation of existing hospitalization
- A persistent or significant incapacity or substantial disruption of the ability to conduct normal life functions
- A congenital anomaly/birth defect
- Important Medical Events (IME) that may not result in death, be life threatening, or require hospitalization may be considered serious when, based upon medical judgment, they may jeopardize the patient or subject and may require medical or surgical intervention to prevent one of the outcomes listed in this definition.

Note: Hospital admission for a planned procedure/disease treatment is not considered an SAE.

SAE reporting is required as soon as the participant signs consent. SAE reporting is required for 30-days after the participant's last investigational treatment or intervention. Any events that occur after the 30-day period and that are at least possibly related to protocol treatment must be reported.

Please note: Any SAE that occurs prior to the start of investigational treatment/intervention and is related to a screening test or procedure (i.e., a screening biopsy) must be reported.

All SAEs must be submitted in PIMS. If an SAE requires submission to the IRB office per IRBSOP RR-408 'Reporting of Serious Adverse Events', the SAE report must be submitted within 5 calendar days of the event. All other SAEs must be submitted within 30 calendar days of the event.

The report should contain the following information:

- The date the adverse event occurred
- The adverse event
- The grade of the event
- Relationship of the adverse event to the treatment(s) (drug, device, or intervention)
- If the AE was expected
- Detailed text that includes the following
  - A explanation of how the AE was handled
  - A description of the subject's condition
  - Indication if the subject remains on the study
- If an amendment will need to be made to the protocol and/or consent form
- If the SAE is an Unanticipated Problem

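### Removing nodes that only ICG identifies is part of the study, yet it is not named as a risk or a safety outcome, and the safety tally does not say whether surgical complications count

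*Combined protocol and SAP*

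**What the plan says.** **Extent of surgery.** Section 4.2 states: "All ICG-positive and TcL-positive nodes will be removed". Section 4.3 has all possible draining basins imaged and all fluorescent nodes resected, followed by a gamma probe check for remaining TcL-positive nodes. Section 3.0 describes standard care as removal of the gamma-positive nodes, on average 1-2 sentinel nodes.

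**Benefits and risks.** Under benefits, section 17.1 says of the study that "it may lead to removal of extra lymph nodes for analysis". Its risks paragraph points to section 11.0 and adds: "The potential risks are related to the adverse effects which could be induced by the ICG dye". Every frequency tier in section 11.0 describes people who receive the dye.

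**Safety objective and analysis.** Section 2.1 lists "Safety of ICG injection". Section 4.2 restates it: "Secondary outcomes include the safety of ICG in this clinical scenario". Under secondary objectives, section 14.0 says: "Safety will be analyzed with descriptive statistics of the number and type of adverse reactions encountered", with CTCAE as the reference.

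**Collection.** Section 9.0 plans intra-operative monitoring for reactions to ICG, and a post-operative evaluation with an adverse event interview at Visit 3 (day 7-28). In section 17.3, "SAE reporting is required for 30-days after the participant's last investigational treatment or intervention", starting from consent. Later events are reportable if at least possibly related, and each SAE report states the relationship to drug, device or intervention.

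**The concern.** A node that fluoresces but is not gamma-positive is removed because of the study. The protocol foresees this, counts it as a benefit, and then ties risk to the dye. Its risk statement therefore does not match its own resection rule.

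The safety objective has the same narrow wording. Section 3.0 looks ahead to eliminating TcL if ICG proves non-inferior, so the safety result will be read as evidence about ICG-guided biopsy as a procedure. If the report covers dye reactions and is silent or unclear about complications of the dissection that ICG prompted, it cannot support that reading.

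**Working it through.** The only computed figure in the plan is N = 59, used here just as a denominator. It reproduces with one-sided alpha 0.05, 80% power, 95% detection for both methods and a 10% margin: n = (1.645 + 0.842)² × (2 × 0.95 × 0.05) / 0.10² = 6.18 × 9.5 = 58.7, rounded up to 59. Nothing below changes it. The rest is mainly a comparison of sections.

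1. **Does the study add surgery?** Standard care (3.0) takes TcL-positive nodes. The study (4.2, 4.3) takes the union of TcL-positive and ICG-positive nodes. The difference is the ICG-positive, TcL-negative nodes. Because all possible basins are imaged, a further basin is possible. One qualification applies: if TcL fails, standard care repeats the mapping 2-3 weeks later (3.0), whereas the study proceeds on ICG alone (4.2). In those patients every node is ICG-only without necessarily being additional surgery.

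2. **Does the risk text match?** No. Sections 11.0 and 17.1 name dye effects only, and the extra nodes appear only under benefits.

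3. **Does the safety analysis include surgical complications?** This is unclear. Sections 9.0 and 13.0 use the term adverse reaction for reactions to ICG. Section 14.0 uses it without that qualifier and refers to CTCAE. Either reading is open.

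4. **Would such events be collected?** Often, yes. The Visit 3 interview is general and SAE reporting is not limited to the dye. The attribution item, however, is specified only for SAEs; no such item is given for non-serious complications.

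5. **Is there a link to ICG-only nodes?** Section 4.3 records ICG and TcL status for every node removed. Section 14.0 uses node-level information to compare counts (Wilcoxon signed-rank), to compare patients with a tumour-positive node (McNemar) and to relate intensity to pathology (logistic regression). None of these involves complications.

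6. **Size in one patient (illustration).** One ICG-only node on a base of 2 is 1/2 = 50% more; on a base of 1 it is 1/1 = 100% more.

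7. **Follow-up.** Assume the SAE window is counted from surgery on day 0. Visit 3 on day 28 leaves 30 − 28 = 2 days; on day 7 it leaves 30 − 7 = 23 days.

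8. **What a tally could show.** With no events in m patients, the exact one-sided 95% upper bound is 1 − 0.05^(1/m). For all 59 patients it is 5.0% (6.1% as the upper limit of a two-sided 95% interval). The number with ICG-only nodes is not given. For assumed values of m = 10, 20 and 30 the one-sided bound is 25.9%, 13.9% and 9.5%. The chance of at least one event in 59 is 1 − (1 − p)^59:

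| Assumed true rate p | Chance of at least one event |
|---|---|
| 1% | 45% |
| 3% | 83% |
| 5% | 95% |
| 10% | 99.8% |

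**The case against.** The strongest reply is that the safety net is wider than the objective. Visit 3 includes a general post-operative evaluation and interview, SAEs are reportable from consent to day 30 whatever their cause, and their attribution can name the intervention. Section 16.1.1 lists operative reports as source documents, and nothing in section 14.0 limits the tally to the dye. This stands against three stronger readings that a reader might infer.

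- *That surgical harm is left out of the safety conclusion.* The documents do not establish this. Section 14.0 is ambiguous and does not exclude such events.
- *That a complication in an ICG-only basin would be classed as routine surgery.* No section says so, and for serious events the attribution item points the other way.
- *That families are told the risk comes only from the dye.* The consent form is not available for review, and section 17.1 requires it to explain the risks fully. The point rests on the protocol text alone.

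A further reply is that a table by ICG-only removal cannot attribute harm. That is also right: every patient has the union of nodes removed, so there is no TcL-only group, and the split is non-randomised and small. The table can describe the surgical cost of the extra nodes but cannot estimate an effect.

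None of this answers the mismatch between the risk statement and the resection rule, or the missing definition of what counts as a safety event.

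**Conclusion.** The point holds as a gap in the stated risk and in the definition and analysis of safety. It does not show that events would go uncollected. The protocol's risk text contradicts the surgery it describes, surgical complications are not named as a safety outcome, section 14.0 does not settle whether they count, and no analysis ties them to ICG-only removal.

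The size across the trial cannot be stated, because the documents give no frequency of ICG-only nodes or basins and no complication rate. A reader might take 50-100% more nodes as the typical effect. It is only the arithmetic for a patient with exactly one ICG-only node. The follow-up gap of 2 to 23 days is minor: it is a gap in planned contact, and the duty to report SAEs continues through day 30. The sample size and the primary analysis are unaffected.

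**What to change.** No change to the resection rule is proposed.

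1. **Sections 11.0 and 17.1.** Reconcile the risk text with sections 4.2 and 4.3: list removal of additional nodes as a study-related risk and delete the sentence that ties risk to the dye alone.
2. **Sections 2.1 and 14.0.** State that safety covers both ICG injection and ICG-guided node removal, and that wound and lymphatic complications are counted and graded by CTCAE.
3. **Visit 3 and section 14.0.** Record these complications by basin at the existing visit. Report the number of ICG-only nodes and basins per patient, from the node-level status already recorded, and tabulate complications by whether ICG-only nodes were removed. Show patients with TcL failure separately. Label the table descriptive because there is no TcL-only group.
4. **Follow-up (minor).** Check records through day 30 for SAEs.

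The cost is an amendment to be approved at each site, a few CRF fields, one table and a record check. The downside is that more events will be listed against the study intervention.
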